1. SUMMARY OF THE STUDY

According to the Tokyo 2018 acute cholecystitis diagnosis and treatment guideline, there is currently no definite conclusion about when patients diagnosed with Grade II acute cholecystitis should be operated on. In this study, two different treatment methods, which have been applied before in the literature and whose superiority has not been clearly proven, will be compared. The patients will be operated in the early (first 7 days) and late (>6 weeks) periods and the difference between the two groups in terms of difficult cholecystectomy, mortality and morbidity will be compared.

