2. PURPOSE OF THE STUDY

Acute cholecystitis is a gallbladder pathology that can lead to serious complications, and Tokyo 2013 and 2018 acute cholecystitis and acute cholangitis diagnosis and treatment guidelines have been published in order to be applied in the diagnosis phase. In these guidelines, patients were divided into three groups based on clinical findings, laboratory findings, and imaging findings, and these groups were named as Grade I, Grade II, and Grade III. While early cholecystectomy is recommended in Grade I patients, treatment options such as early cholecystectomy, late cholecystectomy after antibiotic therapy, and late cholecystectomy after cholecystostomy are left to the discretion of clinicians in Grade II high-risk and Grade III patients, depending on the clinical condition of the patient. Although there is no definite opinion about which treatment is superior today, the studies included patients in all three stages. In addition, most of the studies in the literature have been carried out retrospectively, and the number of prospective studies is very few. In this study, we will examine whether there is a significant difference in terms of difficult cholecystectomy, mortality and morbidity between early and late cholecystectomy in Grade II patients who are most difficult in the decision stage.

Koetsu Inoue et al. reported that there are fewer technical difficulties in cholecystectomies performed within the first 96 hours after admission with the diagnosis of acute cholecystitis (1).

In contrast, Yun-Xiao Lyu et al. showed that there is a significant difference between cholecystectomy performed at the first admission and cholecystectomy performed in the late period, only in terms of length of hospital stay (2). Ismael Mora-Guzmán et al. also reported in their study that there was no significant difference in complications between early and late cholecystectomy(3). Again, Vinoban Amirthalingam et al. It has been reported that early period cholecystectomy can be performed safely in Grade II and III patients (4). In all these studies, no clear distinction was made for early and late cholecystectomy, and both techniques were shown to be applicable.

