3. EXPECTED BENEFITS AND RISKS FROM THE RESEARCH

In this study, there is no expected risk since a different treatment method and medication will not be tried in previous similar studies. As a result of this study, if there is a difference between the research groups, new data will be obtained in terms of the approach to Grade II acute cholecystitis in the literature. Due to the limited number of prospective studies on this subject, the data to be obtained may change the treatment scheme to be applied in the future for the patient population in the research group and may benefit from reducing the complication rates.

4. TYPE, SCOPE, DESIGN AND THE DATA TO BE OBTAINED AFTER THE RESEARCH STATISTICAL TO BE USED IN THE EVALUATION METHODS

The research was planned as a prospective study. The study is single-centered and the patient group graded as Grade II according to the Tokyo 2018 guideline acute cholecystitis diagnostic criteria will be included in the study. Grade I and III patients, patients with accompanying choledocholithiasis, patients who are pregnant or likely to become pregnant, patients who cannot comply with the treatment due to their mental status and who cannot sign their own consent for treatment will not be included in the study. Patients classified as Grade II acute cholecystitis will be informed about the treatment options and possible complications after hospitalization. Patients will decide on the treatment method to be applied with their consent. The patients will be divided into two groups as those operated in the early period (first 7 days) and those operated in the late period (>6 weeks). The parameters to be compared were the rate of conversion from laparoscopic to open, bile duct injury and bile leakage rate, grade II-III complication rate in the Clavien Dindo complication scoring system, morbidity rate in the first 30 days postoperatively, and difficult cholecystectomy rate based on intraoperative imaging findings according to the Parkland scoring system. The research will be terminated when the number of 120 patients determined by the power analysis result is reached.

Chi-square and Student's t test will be used for the statistical evaluation of the results of the patients, respectively, for quantitative and continuous variables, and Mann-Whitney U test (two samples) or Kruskal-Wallis test (more than two samples) will be used for the analysis of abnormally distributed variables.

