5. THE NUMBER OF PATIENTS AND VOLUNTEERS TO BE INCLUDED IN THE RESEARCH QUALITY AND JUSTIFICATION OF SELECTION (AGE RANGE, GENDER ETC.).

The research population was determined as 120 patients as a result of the power analysis results. The number of volunteers will be 120, and the patient group graded as Grade II according to the Tokyo 2018 guideline acute cholecystitis diagnostic criteria will be included in the study, regardless of gender group over the age of 18.

6. PARAMETERS TO LOOK AT AND WHERE TO LOOK AT THE PARAMETERS AND BY WHOM

Parameters to be checked: Age, gender, comorbid diseases, previous abdominal operations, drug allergy, ASA score, Parkland score, length of hospital stay, duration of operation, amount of bleeding during the operation, type of operation, biliary tract complication, Clavien Dindo complication score, postoperative mortality and morbidity. The parameters will be checked and recorded by the principal investigator during the application and follow-up.

7. WHICH PARAMETERS TO BE USED IN THE RESEARCH ARE ROUTINE FOR THAT DISEASE GROUP AND WHICH ARE SPECIALLY REQUESTED FOR THE RESEARCH

Among the parameters and tests used in the research, there are no specific ones used for the research, and all of them are recorded and requested during the routine follow-up of the disease.

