8. PROJECTED WORKING TIME, START AND END DATES

The duration of the study was planned as 18 months, and the study date range was determined as 14.12.2019-14.06.2021.

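### Morbidity is counted only from surgery, and only in patients operated on in one of the two time bands, so the harms of waiting for late surgery are left out of the comparison

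*Combined protocol and SAP*

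**What the plan says.** The aim carries no postoperative limit. Section 1 says "the difference between the two groups in terms of difficult cholecystectomy, mortality and morbidity will be compared", and section 2 asks "whether there is a significant difference in terms of difficult cholecystectomy, mortality and morbidity between early and late cholecystectomy". Section 3 hopes that "the data to be obtained may change the treatment scheme to be applied in the future".

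The outcome definitions are narrower. Section 4 gives one window, "morbidity rate in the first 30 days postoperatively". Section 6 lists "Clavien Dindo complication score, postoperative mortality and morbidity" among the recorded parameters. The Clavien-Dindo grade II-III rate, biliary complications and length of stay have no stated window. Nowhere does the plan name recurrent attacks, readmissions, unplanned drainage or surgery, or death before the operation as outcomes.

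On allocation, section 4 says "Patients will decide on the treatment method to be applied with their consent" and then describes the groups as "those operated in the early period (first 7 days) and those operated in the late period (>6 weeks". Neither day 0 nor an upper limit for the late period is given. Sections 4 and 9 end the research when 120 patients are reached, without separating enrolment from follow-up. In section 8, "the study date range was determined as 14.12.2019-14.06.2021".

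**The concern.** Waiting is part of late treatment. Whatever happens to a patient during the wait is a consequence of choosing late surgery, and an outcome that starts at the operation cannot see it. The same clock also omits pre-operative events in the early group, but over a much shorter time, so the omission does not cancel.

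The group definition makes this worse. A patient enters the late group only after coming through six weeks and being operated on. Those in whom waiting failed leave the comparison altogether, and a longer outcome window alone would not bring them back.

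At stake is the study's stated use. A result that tends to flatter late surgery could be read as guidance on when to operate. Analysis cannot repair it afterwards if waiting-period events and unoperated patients were never recorded.

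**Working it through.** **1. Day counts from the plan's own definitions.** Assume both periods run from admission or symptom onset, which the plan does not say.

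| | Early | Late |
|---|---|---|
| Pre-operative time not counted | at most 7 days | more than 42 days |
| Postoperative window | 30 days | 30 days |
| Window closes, from day 0 | by day 7 + 30 = 37 | after day 42 + 30 = 72 |

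The uncounted time differs by more than 42 − 7 = 35 days, a ratio of more than 42/7 = 6.

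**2. Illustration of size.** The documents give no event rates, so every rate here is assumed.

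- Waiting-period risk over 42 days: w = 5, 10, 15, 20, 25%.
- The same daily risk over the 7 days before early surgery: wE = 1 − (1 − w)^(7/42) = 0.9, 1.7, 2.7, 3.7, 4.7%.
- Postoperative morbidity: pE (early) and pL (late).
- Early total = 1 − (1 − pE)(1 − wE). Late total = 1 − (1 − pL)(1 − w).

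For pE = 20% and pL = 12%, the planned late-minus-early difference is −8.0 points. With pre-operative events counted in both groups:

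| w | Early total | Late total | Late − early |
|---|---|---|---|
| 5% | 20.7% | 16.4% | −4.3 |
| 10% | 21.4% | 20.8% | −0.6 |
| 15% | 22.1% | 25.2% | +3.1 |
| 20% | 22.9% | 29.6% | +6.7 |
| 25% | 23.7% | 34.0% | +10.3 |

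The sign changes where 0.80(1 − w)^(1/6) = 0.88(1 − w), that is (1 − w)^(5/6) = 0.80/0.88, giving w = 10.8%. With no early pre-operative risk it is 1 − 0.80/0.88 = 9.1%. With wE fixed at 5% it is 1 − 0.80 × 0.95/0.88 = 13.6%.

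With equal postoperative rates of 15%, a planned difference of 0 becomes +3.5, +7.0, +10.5, +13.9 and +17.3 points.

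Over four assumed pairs (pE, pL) = (20, 12), (15, 15), (20, 20) and (12, 20)%, the shift against late surgery is 3.3 to 3.7 points at w = 5%, 6.5 to 7.4 at 10%, and 15.9 to 18.3 at 25%.

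**3. Effect on a test.** Pooled two-proportion z, assuming 60 per group (the plan gives only the total of 120).

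- (20, 12): as planned, z = 1.20, p = 0.23. At w = 25% (23.7% v 34.0%), z = 1.24, p = 0.22. The estimate changes sign, but no row of the table is significant.
- (15, 15): p = 1.00 as planned, p = 0.034 at w = 25%.
- (12, 20): p = 0.23 as planned, then 0.022, 0.009 and 0.004 at w = 15, 20 and 25%.

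**4. Direction.** Counting pre-operative events moves the difference against late surgery whenever w(1 − pL) > wE(1 − pE). This holds in every case above.

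**5. Calendar.** For follow-up to finish by 14.06.2021, the last index admission falls on 3 April 2021 for 72 days, 2 April for 73, 16 March for 90 and 14 February for 120.

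**The case against.** The best defence is that this is a comparison of operations. Section 2 speaks of early and late cholecystectomy. Difficult cholecystectomy comes first in the aim, and conversion, bile duct injury and Parkland grade are operative outcomes that a morbidity window does not touch. For that question, 30-day postoperative morbidity is coherent. This stands, and is why the outcome should be kept. It does not settle the matter: section 1 describes two treatment methods, and section 3 looks to changing treatment.

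Second, some waiting-period events might still be captured. The Clavien-Dindo rate, biliary complications and length of stay have no window, and section 6 has parameters recorded at application and during follow-up. That is possible, but nothing says such events are collected or analysed, and mortality and morbidity are expressly labelled postoperative.

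Third, the size rests on assumed rates and a constant daily risk. If risk is concentrated in the first days, wE rises and the shift shrinks. This is right, and the figures should be read only as a range. The unequal uncounted time does not depend on them.

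Fourth, who is in each group is a separate question from when the clock starts. That is fair, but both faults remove the same events, and correcting only one leaves the comparison biased.

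**Conclusion.** The concern holds and should be fixed before the results are used to compare early with late treatment. As written, the plan leaves more than 42 pre-operative days uncounted in the late group against about 7 in the early group, and excludes patients in whom waiting failed. The day counts follow from the plan's own definitions, given a day 0 at admission or onset.

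The likely direction favours late surgery, subject to the inequality in the working. The size cannot be derived from the documents. Under the assumed rates it is roughly 3 to 18 points: enough to reverse the sign of an 8-point advantage for late surgery once the waiting risk passes about 11%, and in some scenarios enough to make a non-significant difference significant. These figures do not include the further effect of patients who fall into neither group.

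**What to change.** 1. Define the groups by the strategy chosen at the index admission, so that patients who die, never return, or are operated on between day 7 and week 6 stay in their group. State day 0.
2. Add a morbidity and mortality outcome counted from the index admission over one common period for both groups, long enough to include 30 days after late surgery. The floor is more than 42 + 30 = 72 days. Because the late period has no upper limit, the sponsor must state the length. List waiting-period complications, readmissions, unplanned interventions and deaths as events.
3. If length of stay is compared, define it as total days over all related admissions in that period.
4. Keep 30-day postoperative morbidity as a separate outcome, labelled as describing the operation.
5. State that reaching 120 patients stops enrolment, not follow-up.

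None of this alters treatment or the timing of surgery. The cost is wording, plus record follow-up at one centre. All patients, including those never operated on, must be asked about admissions elsewhere at the end of the period. Late patients already need more than 72 days under the current plan, so the added burden is the longer follow-up of early patients, contact with unoperated patients, and any time beyond the floor. Enrolment must close by the dates in the working, or the study end date must be extended.

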9. WITHDRAWAL AND TERMINATION CRITERIA

When patients want to leave the study, they can leave the study provided that they inform the principal investigator. The research doctor, who is also the coordinator of the study, may remove the patient from the study without informing the patient due to my negligence in fulfilling the requirements of the study program or in order to improve the quality of the medical care I am receiving.

The research will be terminated if the determined population (even earlier than the determined date) is reached.

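### Does using 120 as the power-analysis result, the number of volunteers and the stopping number leave the comparison short of patients?

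*Combined protocol and SAP*

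**What the plan says.** One figure does three jobs. It is the result of the power analysis (Section 5: "The research population was determined as 120 patients as a result of the power analysis results"), the number of volunteers (Section 5: "The number of volunteers will be 120") and the stopping number (Section 4: "The research will be terminated when the number of 120 patients determined by the power analysis result is reached"). Section 9 repeats the stopping rule: "The research will be terminated if the determined population (even earlier than the determined date) is reached".

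The groups in Section 4 are defined by when surgery took place: "those operated in the early period (first 7 days) and those operated in the late period (>6 weeks". No group is named for patients operated on between those windows or not operated on at all.

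Section 9 provides for losses. On the patient's side, "When patients want to leave the study, they can leave the study provided that they inform the principal investigator"; on the investigators' side, the research doctor "may remove the patient from the study without informing the patient". No expected loss rate or replacement rule is given. Section 7 says of the study's measurements that "all of them are recorded and requested during the routine follow-up of the disease".

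**The concern.** The number recruited and the number compared look as if they have been treated as the same thing. A patient who consents can still withdraw, be removed, be operated on between the two windows, or never be operated on. None of these patients enters either group. Someone who chooses late surgery has more than 6 weeks in which this can happen, so losses might be expected mainly on that side, although the documents do not say so.

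If 120 is needed in the analysis and is counted at consent, the comparison falls short and precision suffers. If 120 is counted at surgery, the comparison is complete, but more than 120 people may have to consent, which sits awkwardly with Section 5. Patients who leave the late pathway would then be replaced and would appear in neither group.

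**Working it through.** **1. Can the plan's 120 be reproduced?** No. Section 5 gives only the result; no significance level, power, event rates, endpoint or allocation ratio is stated. The usual two-proportion formula (two-sided 5%, equal groups, no continuity correction) is, per group,

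n = [1.960·√(2p̄(1−p̄)) + z·√(p₁(1−p₁) + p₂(1−p₂))]² / (p₁−p₂)²,

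where p̄ is the mean of p₁ and p₂, and z is 0.842 for 80% power or 1.282 for 90%. Many unstated inputs land near 120 in total:

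- 20% vs 44% at 80% power: 118
- 30% vs 55% at 80% power: 122
- 30% vs 59% at 90% power: 120

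So 120 can be neither confirmed nor refuted. Nor can it be shown to lack an allowance: a requirement of 108 evaluable patients with 10% loss gives 108/0.90 = 120 exactly.

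**2. What would loss cost if 120 were the evaluable number, counted at consent?** All inputs other than 120 are assumptions. Let p be the share choosing late surgery and L the share of those lost to the comparison. All early-choosers are taken to be operated on within 7 days, nobody moves between groups, and outcome variance is equal.

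- Number compared = 120(1 − pL)
- Standard error ratio = √{[1/(1−p) + 1/(p(1−L))] / [1/(1−p) + 1/p]}
- Power, if a full 120 gave 80% = Φ(2.802/ratio − 1.960)
- Consenting patients needed for 120 operated on = 120/(1 − pL), rounded up

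With p = 0.5:

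| L | Compared | SE ratio | Power | Consenting for 120 operated on |
|---|---|---|---|---|
| 0% | 120 | 1.000 | 80% | 120 |
| 5% | 117 | 1.013 | 79.0% | 124 |
| 10% | 114 | 1.027 | 77.8% | 127 |
| 20% | 108 | 1.061 | 75.2% | 134 |
| 30% | 102 | 1.102 | 72.0% | 142 |

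Worked line for L = 20%: 120(1 − 0.10) = 108; ratio = √[(2 + 2.5)/4] = 1.061; 2.802/1.061 − 1.960 = 0.68, and Φ(0.68) = 0.752; 120/0.90 = 133.3, so 134.

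**3. How firm are these figures?** Not firm. If both groups lose patients at the same rate, power is Φ(2.802·√(1−d) − 1.960): 78.0%, 75.7%, 70.7% and 65.0% for d = 5%, 10%, 20% and 30%. Crossing a late share of 30% to 70% with late losses of 5% to 30%, the number consenting for 120 operated on runs from 120/(1 − 0.015) = 121.8, so 122, to 120/(1 − 0.21) = 151.9, so 152. A late-chooser who is operated on within 7 days would join the early group and not be lost at all. An early-chooser who passes day 7 without surgery would be lost, and the table sets those losses to zero.

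**4. Is there a fixed power for losses to erode?** Patients choose their treatment, so the split is not controlled. With no losses, a 70/30 split of 120 gives Φ(2.802·√0.84 − 1.960) = 72.8%, against 80% at an even split. That is about the same as a 30% loss confined to the late group.

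**5. The two readings side by side.** Counted at surgery, the comparison has its 120, and the only tension is the word for volunteers in Section 5, which the plan never defines. Counted at consent, the comparison has however many were operated on in the two windows, and that number will be known and reported. On either reading the tests in Section 4 are the same.

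**The case for a change.** The best case for acting is that a stopping rule should say what it counts. Nothing in Sections 4, 5 or 9 does so, and repairing this takes only a few words. Section 9 expects some patients to leave, and the late pathway gives them time to do so. Continuing until 120 have been operated on does not fully reconcile the text either: with any loss before surgery more than 120 would have consented, and Section 5 can be read as ruling that out. If those who leave are not reported, a reader could not see them.

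Most of this stands as description. The counting event is undefined, no allowance is stated, and a full account of consenting patients by chosen treatment would be good reporting. It does not establish that the plan fails at something it sets out to do. The shortfall exists only if two unstated things hold together: 120 is the evaluable number, and it is counted at consent. The conflict with Section 5 exists only if volunteers means everyone who consents. Section 1 describes the patients as people who will be operated on early or late, and Section 4 divides the patients into two operated groups, which fits a count of operated patients at least as well. Whether replacing late-choosers who leave would bias the comparison cannot be judged from the documents. An account of those patients belongs in the report and changes no planned test.

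**Conclusion.** No change follows. The plan leaves unsaid whether 120 is a consented, operated or fully followed number and whether it includes an allowance for loss. That is a gap in wording which investigators will settle in practice, either by counting operated patients to 120 or by analysing those operated on among 120 enrolled and giving the actual number.

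The possible cost is imprecision. It ranges from none (no loss, an allowance already built in, or counting at surgery) to roughly 1 to 8 percentage points of power for late-group losses of 5% to 30%, and 2 to 15 points if both groups lose at those rates. These sizes rest on an assumed 80% power at 120, an assumed even split and assumed loss rates; the documents supply none of them. With no stated power or loss rate, there is no design target that 120 can be shown to miss.

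Incomplete follow-up of the last patients is not a serious worry, because Section 7 has every measurement collected in routine care. The available remedies are to write down a definition or an allowance, to enrol more patients on a guessed loss rate, or to add a patient account to the report. None of these alters an analysis the plan describes.

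### Student's t is specified for continuous variables although group sizes are left to patient choice; if the smaller group is also the more variable, its error rate departs from 5%, and Welch's t would hold it

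*Combined protocol and SAP*

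**What the plan says.** Section 4 pairs chi-square and Student's t with two kinds of variable. It states that chi-square and Student's "t test will be used for the statistical evaluation of the results of the patients", assigned in turn to what it calls quantitative and continuous variables, which I read as chi-square for categorical variables and Student's t for continuous ones. The alternative is for non-normal data: "Mann-Whitney U test (two samples) or Kruskal-Wallis test (more than two samples) will be used for the analysis of abnormally distributed variables". No unequal-variance version of the t test is mentioned.

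On group formation, Section 4 states: "Patients will decide on the treatment method to be applied with their consent". The two groups are early surgery (first 7 days) and late surgery (more than 6 weeks). Only the total is fixed: "The research will be terminated when the number of 120 patients determined by the power analysis result is reached". Section 5 repeats the 120 without a ratio or a per-group target.

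The outcomes that Section 4 lists for comparison are all rates: conversion to open surgery, bile duct injury and leakage, Clavien-Dindo II-III complications, 30-day morbidity and difficult cholecystectomy. Continuous variables appear in Section 6, among the parameters to be recorded: age, length of stay, and "duration of operation, amount of bleeding during the operation".

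**The concern.** Student's t pools the two variances. It keeps its nominal error rate if the groups are of equal size or if their variances are equal. The plan secures neither. Sizes follow patient choice, and the groups are operated on in different disease states, so a different spread of operating time is plausible. That is an inference, because the documents report no SDs.

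When both conditions fail, the pooled standard error is wrong, and the direction depends on which group is smaller. If the smaller group has the larger SD, the standard error is too small and false positives rise. If the larger group has the larger SD, it is too large and the test loses power. The normality-based fallback does not catch this: a roughly normal variable with unequal spread stays with Student's t.

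**Working it through.** **The plan's own figure.** The 120 cannot be reproduced, because no alpha, power, effect size, SD or event rate is stated. It is taken as given.

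**Inputs**
- From the documents: N = 120 in total, two groups, Student's t, no fixed split.
- Assumed: two-sided 5%, normal data, splits from 60/60 to 20/100, SD ratios of 1, 1.5 and 2 in either direction.

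**Formulas.** Under equal means, with group sizes n1, n2 and SDs s1, s2:
- true SE = √(s1²/n1 + s2²/n2)
- pooled variance = [(n1−1)s1² + (n2−1)s2²]/(n1+n2−2)
- pooled SE = √[pooled variance × (1/n1 + 1/n2)]
- large-sample error rate of Student's t = 2[1 − Φ(t_crit × pooled SE / true SE)], with t_crit = 1.980 on 118 df

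**Worked case 1: 40/80, smaller group has twice the SD (s1 = 2, s2 = 1)**
- true SE = √(4/40 + 1/80) = √0.1125 = 0.335
- pooled variance = (39×4 + 79×1)/118 = 235/118 = 1.992
- pooled SE = √(1.992 × 0.0375) = 0.273
- 1.980 × 0.273/0.335 ≈ 1.61, giving 10.7%

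**Worked case 2: 40/80, larger group has twice the SD (s1 = 1, s2 = 2)**
- true SE = √(1/40 + 4/80) = √0.075 = 0.274
- pooled variance = (39×1 + 79×4)/118 = 355/118 = 3.008
- pooled SE = √(3.008 × 0.0375) = 0.336
- 1.980 × 0.336/0.274 ≈ 2.43, giving 1.5%

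**Simulation.** 100,000 normal data sets per scenario. The Monte Carlo standard error at 5% is √(0.05×0.95/100,000) ≈ 0.07 points. Type I error of Student's t:

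| Split | Equal SDs | Smaller group more variable, ratio 1.5 | Same, ratio 2 | Larger group more variable, ratio 1.5 | Same, ratio 2 |
|---|---|---|---|---|---|
| 48/72 | 5.0% | 7.1% | 8.3% | 3.5% | 2.8% |
| 40/80 | 5.1% | 8.5% | 11.1% | 2.7% | 1.7% |
| 30/90 | 4.9% | 10.7% | 15.2% | 1.8% | 0.8% |

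At 60/60 it was 4.9-5.2% at every SD ratio tried. Welch's test gave 4.9-5.2% in every scenario. The formula gives slightly lower values than the simulation (10.7% against 11.1%, and 1.5% against 1.7%), as a large-sample approximation would.

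**Cost of Welch when the SDs are equal.** The true difference was set at each split to give about 80% power:

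| Split | Student's t | Welch | Loss (points) |
|---|---|---|---|
| 60/60 | 79.2% | 79.2% | 0 |
| 40/80 | 79.2% | 78.8% | 0.4 |
| 30/90 | 79.1% | 78.1% | 1.0 |
| 20/100 | 79.3% | 77.1% | 2.2 |

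**The case against.** The strongest reply is that this reaches little of the study. Every comparison listed in Section 4 is a rate, and the stated aim (difficult cholecystectomy, mortality, morbidity) needs no t test. Bleeding and length of stay are likely to be skewed and so to go to Mann-Whitney, and operating time may follow them. The splits and SD ratios are the reviewer's assumptions, a mild imbalance does less harm, and Student's t is a conventional choice. All of this stands, and it makes the point minor. It does not remove it: Section 4 does prescribe Student's t for continuous variables, and nothing covers a near-normal variable with unequal spread.

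Four stronger readings are tempting, and none is supported.
- A reader might infer that uneven group sizes alone inflate the error. They do not: with equal SDs it is about 5% at every split.
- A reader might infer that inflation is the expected result. The documents do not say which group will be smaller or more variable, so a conservative test is equally open.
- A reader might infer that the study's main comparisons are compromised. They are rates and are untouched by this.
- A reader might infer that Welch's test is free, or that it repairs the self-selected comparison. It has a small power cost, and it does nothing about confounding.

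**Conclusion.** The point holds as a low-priority, conditional one. With N = 120, a two-sided 5% level, normal data, a 40/80 to 30/90 split and an SD ratio of 1.5 to 2, the error rate of Student's t would be about 8-15% in the adverse direction and about 1-3% in the other. If either the sizes or the SDs turn out equal, there is no problem. The level, splits and SD ratios are assumptions; the documents supply only the total, the test and the absence of a fixed split. The scope is limited to continuous variables from the Section 6 list that are judged near-normal, with duration of operation the clearest candidate.

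**What to change.** In Section 4, replace Student's t test with Welch's t test (unequal variances) for two-group comparisons of continuous variables. Specify it outright, not conditionally on a preliminary variance test, and report each group's size and SD with the result.

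The cost is a short wording change and, if the variances are in fact equal, the small power loss tabulated above. No data collection or sample size changes. Confounding from patient choice needs its own treatment in the plan.
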